3.3.5. Duration of Incident Infection

The duration of incident infection will be defined as the midpoint of the interval between incident HCV infection and viral clearance. The incident HCV infection date will be defined as the midpoint of the interval between the date of the last documented HCV RNA negative result and the date of the first positive HCV RNA result. The viral clearance date will be defined as the midpoint of the interval between the date of the

last test with detectable HCV RNA and the first of two consecutive samples with undetectable HCV RNA. For subjects who do not clear HCV viremia, the duration will be measured as six months following incident infection for the fourth exploratory endpoint.

3.3.6. Baseline Value

The baseline value will be defined as the last value obtained prior to the first vaccination.

3.3.7. Sufficient Follow-up

Sufficient follow-up will consist of at least three clinic visits following the second vaccination. If the second dose of vaccine was not administered, the target date for the second dose will be used in this calculation. Subjects who receive treatment for incident HCV infection will be censored in time to event analyses of chronic infection at the date of first treatment.

4. INVESTIGATIONAL PLAN

4.1. Overall Study Design and Plan

DMID 10-0069 is a Phase I/II double-blind (subject, investigator, and clinical personnel monitoring safety and laboratory assay results, and laboratory personnel), randomized, and placebo-controlled study in approximately 540 individuals at high risk for HCV infection due to active injection drug use (IDU) between the ages of 18 and 45. HCV-uninfected (negative for both anti-HCV and HCV RNA at screening) male and female adults who are current IDUs will be randomized at a 1:1 ratio, stratified by gender and IL28B status, to receive AdCh3NSmut1 and MVA-NSmut HCV vaccines or placebo at Day 0 and Day 56. The study is designed to be implemented in two stages and enroll a total of 270 subjects/group.

Stage 1: Blinded, randomized, controlled assessment of AdCh3NSmut1 and MVA-NSmut HCV vaccine compared to placebo in 68±4 (34±2/group) evaluable subjects. This study stage will evaluate safety of the combined use of both vectors in a prime/boost regimen in the target population. Each individual will be followed with extensive safety and immunogenicity measures. Interim analysis (safety and immune responses) is planned immediately following the end of stage 1 (at Day 63 follow-up (34±2/group) for all evaluable subjects).

Stage 2: After the safety and immunogenicity interim analyses, the study will be extended into a 2nd stage, wherein an additional (n=472±4) HCV-uninfected subjects will be enrolled. A 2nd interim analysis to evaluate progress (statistical and enrollment) toward the efficacy endpoint will occur when roughly one-third of enrolled and currently per-protocol subjects (N = 98) have completed six months of post-vaccination follow-up, but no later than one month prior to the planned completion of enrollment to the trial. Immune responses will be evaluated following each vaccination and HCV viremia status will be monitored monthly for 18 months following the 2nd vaccination. This stage is designed as a blinded, randomized placebo-controlled study, with safety and efficacy assessments.

The planned duration of the study is approximately 63 months total including accrual time for subjects (assuming 31 months of screening/enrollments, plus 3 months of halted enrollment for the first interim analysis), 2 months vaccination, 18 months follow-up of each enrolled subject, and 9 months extended observation (monthly), from the time of infection, for subjects becoming viremic in the last month of follow-up.

The follow-up period for detection of HCV infection will start after the second injection of vaccine and will last 18 months. Subjects who become viremic will be followed for 9 months after detection of HCV (up to month 29). The trial will be considered closed when the observation period for the last subject that became viremic during the 18 months follow-up is completed. A schematic of the general design is provided in [Figure 1](#). [Table 1](#) and [Table 2](#) presents the schedule of events for each visit for subjects with and without confirmed HCV infection.

4.2. Discussion of Study Design, Including the Choice of Control Groups

The choice of the intramuscular route for AdCh3 is based on the assumption that no co-infection of natural human Adenovirus could occur at this site. Furthermore, there is a large body of data from clinical trials in humans using replication defective Ad5- and Ad6-based HIV vaccines injected intramuscularly showing an excellent safety profile, no viral shedding, and high levels of immunogenicity. MVA-NSmut will also be given by the intramuscular route because it is better tolerated than when administered by subcutaneous route. The vaccine schedule will consist of a single priming injection with AdCh3NSmut1, followed by a single boost with MVA-NSmut 56 days later in a heterologous prime/boost regimen. This is based on promising data

from ongoing malaria clinical trials in Oxford, where optimal immunogenicity is achieved with an 8 week interval between vectors and from pre-clinical data shown in the previous section. The choice of placebo for the comparator is due to the non-existence of a HCV vaccine.

4.3. Selection of Study Population

4.3.1. Subject Inclusion Criteria

Subjects eligible to participate in this study must meet all of the following inclusion criteria prior to the first vaccination:

1. Comprehension of informed consent.
2. 18-45 year old men or women with acknowledged active IDU in the past 90 days and have no travel plans that would interfere with ability to meet the study visit schedule.
3. In good general health as determined by a participating study physician and results within acceptable ranges for clinical laboratory evaluations as detailed in Appendix A.
4. Negative for antibodies to hepatitis C virus (anti-HCV).
5. Negative for HCV RNA.
6. Negative antibodies to HIV.
7. Negative for HBsAg.
8. Able and willing (in the Investigator's opinion) to comply with all study requirements.
9. Willing to allow the investigators access to their medical records.
10. Willingness to practice continuous effective contraception from the screening visit through 90 days after the last vaccination (males and females).
11. Among females, a negative pregnancy test within 24 hours prior to vaccination.
12. Agreement to refrain from blood donation during the course of the study or after the study.
13. Provide written informed consent prior to initiation of any study procedures.
14. Willing to provide contact information for study follow-up activities, including the address, name and contact information of three people who can be contacted to facilitate follow-up compliance.

4.3.2. Subject Exclusion Criteria

Subjects eligible to participate in this study must not meet any of the following exclusion criteria prior to first vaccination:

1. The subject is currently participating in a study that involves an experimental agent (vaccine, drug, biologic device, blood product, or medication) or has received an experimental agent within 30 days prior to enrollment in this study, or expects to receive another experimental agent during participation in this study.
2. Prior receipt of a recombinant simian or human adenoviral vaccine or MVA vaccine.
3. Administration of immunoglobulins and/or any blood products within the 90 days preceding the planned administration of the vaccine candidate.

4. Any confirmed or suspected immunosuppressive or immunodeficient state, including: HIV infection; asplenia; recurrent, severe infections.
5. History of allergic disease or reactions likely to be exacerbated by any component of the vaccine (i.e., known hypersensitivity to aminoglycoside antibiotics or to egg proteins).
6. History of clinically significant contact dermatitis or other significant dermatological conditions such as psoriasis.
7. Any history of anaphylaxis in reaction to vaccination.
8. Pregnancy, lactation or willingness/intention to become pregnant during the study.
9. History of cancer (except for successfully treated basal cell carcinoma of the skin and cervical carcinoma in situ).
10. History of severe psychiatric illness, including severe depression, history of suicidal ideation, suicidal attempts, or psychosis requiring medication. The subject has a diagnosis of schizophrenia, bi-polar disease, or other severe (disabling) chronic psychiatric diagnosis that is uncontrolled and would interfere with the ability to adhere to the protocol.
11. Any other serious chronic illness requiring hospital specialist supervision.
12. Suspected or known current alcohol abuse as defined by a score of 10 or more on the Alcohol Use Disorders Identification Test (AUDIT) C test (a standardized screening tool used to identify hazardous drinkers or those with active alcohol use disorders, including abuse or dependence).
13. At high risk of HIV infection by the following criteria (adapted from HIV Network for Prevention Trials (HIVNET) behavioral criteria for high risk of HIV): (1) sexually active male who has sex with men (MSM), defined as (i) male who has had anal sex with male sexual partner or partners in the past year or (ii) a male who exchanged sex with male partner(s) for money or drugs in the past year; and (2) female and in a current relationship with a high risk male (active MSM, HIV positive male).
14. Any other significant disease, disorder or finding, which, in the opinion of the Investigator, may put the subject at risk because of participation in the study, may influence the result of the study, or may influence the subject's ability to participate in the study.
15. History of or current diagnosis of Diabetes mellitus.
16. History of or current diagnosis of autoimmune disease.
17. History of or current cardiac disease including history of myocardial infarction or arrhythmia.
18. Current diagnosis of active liver disease.
19. History of seizure disorder or currently taking anti-convulsant therapy that would interfere with safety evaluation.
20. Uncontrolled hypertension (defined as systolic blood pressure being greater than 140mm Hg or diastolic blood pressure being greater than 90mm Hg).
21. History of splenectomy.
22. Long term immunosuppressive use (defined as taken for 14 days or more in total at any time during the past 180 days) of high dose oral or parenteral glucocorticoids (high dose defined as prednisone \geq 20 mg total daily dose, or equivalent dose of other glucocorticoids); or high-dose inhaled steroids

(high dose defined as >800 mcg/day of beclomethasone dipropionate or equivalent); or any use of hepatotoxic or non-FDA approved medication.

23. Have an acute illness, including an oral temperature greater than or equal to 100.4°F, within 7 days prior to the first vaccination.
24. Immunization against another pathogen within 14 days of planned injection.

The following events associated with vaccine immunization constitute absolute contraindications to further administration of vaccine. The subject will not receive additional vaccination, but will continue with scheduled follow-up procedures except vaccination.

1. Anaphylactic reaction following administration of vaccine.
2. Pregnancy. If a woman reports having a positive home urine pregnancy test or a positive in clinic urine pregnancy test prior to a scheduled second vaccination, she is not eligible to receive the study vaccine. If she later returns to clinic and reports having a negative home urine pregnancy test and this is confirmed by a negative in clinic urine pregnancy test and a negative blood pregnancy test she may be eligible for the second vaccination if she is still within the vaccination window and no other exclusion criteria are met.

The following adverse events constitute contraindications to administration of vaccine at that point in time. If any one of these adverse events occurs at the time scheduled for vaccination, the subject may be vaccinated at a later date (within 28 days of scheduled administration) or withdrawn at the discretion of the investigator. The subject will not receive additional vaccination, but will continue with all scheduled follow-up procedures except vaccination.

1. Acute disease at the time of vaccination (acute disease is defined as the presence of a moderate or severe illness with or without fever). The vaccine dose can be administered to persons with a minor illness such as diarrhea, mild upper respiratory infection with or without low-grade febrile illness, i.e., temperature of <38°C (100.4°F).
2. Temperature of >38°C (100.4°F) at the time of vaccination.
3. Immunization against another pathogen within 14 days of vaccination.

If a subject is withdrawn from the study, all study procedures (except for another vaccination) including safety follow-up will be continued, if possible. If voluntary withdrawal occurs, the subject will be asked to continue scheduled study procedures (except for another vaccination) including safety evaluations, if possible, and be given appropriate care under medical supervision if symptoms of any AE related to participation in the study are continuing. The subject will be followed until the AE is resolved or until the subject's condition becomes stable. (Note: These plans regarding follow-up only apply if the subject received at least one study dose.) Any subject whose vaccinations have been discontinued will be seen for appropriate follow-up visits or medical care will be arranged until the adverse event has resolved or stabilized.

4.4. Treatments

4.4.1. Treatments Administered

Two investigational vaccines will be used in this study, namely AdCh3NSmut1 and MVA-NSmut, along with the 0.9% sodium chloride as placebo.

4.4.2. Method of Assigning Subjects to Treatment Groups (Randomization)

Enrollment of subjects is done online using the enrollment module of the EDC, maintained by the SDCC. Eligible subjects are randomized and assigned in a 1:1 ratio stratified by site, gender, and IL28B status, to receive AdCh3NSmut1 and MVA-NSmut HCV vaccines or placebo at Day 0 and Day 56 after providing consent and confirmation of eligibility with the study inclusion and exclusion criteria.

4.4.3. Selection of Doses in the Study

Vaccine Doses: In this study AdCh3NSmut1 vaccine will be administered at 2.5×10^{10} vp, and MVA-NSmut at 1.8×10^8 pfu.

AdCh3NSmut1: Clinical data are not available for the AdCh3NSmut1 vector. AdCh3NSmut1 has minimal changes from AdCh3NSmut vector used in the Okairos' 3 on-going clinical trials with NSmut Antigen HCV Vaccine. Pre-clinical assessment has shown that these changes do not affect the safety or immunogenicity profile. Safety data from the study HCV001 and the ongoing HCV003 have shown that AdCh3NSmut is safe and well tolerated in healthy subjects at the dosage (2.5×10^{10} vp) selected for this study.

Phase I studies assessing safety and immunogenicity in healthy individuals of Ad5- and Ad6-based HIV vaccine candidates were shown to induce higher rates of responses and more potent responses when they were administered at 10^{10} vp/dose versus 10^9 vp/dose. Similarly, there was a greater frequency of detectable cellular responses after 6 months from the first administration of the vector in the higher dose groups (between 10^{10} and 10^{11} vp/dose). These studies have shown that adenoviral vectors are safe and well tolerated up to 10^{11} vp/dose with some more reactogenicity associated with the highest dose.

MVA-NSmut: In this study, MVA-NSmut will be administered at 1.8×10^8 pfu. This dose has been selected based on the use of MVA vectors in primate and human studies. In Oxford, MVA malaria vaccines have been safely administered in multiple Phase I and Phase II studies at 2×10^8 . MVA ME-TRAP and MVA-vectored P. falciparum CS protein has been well tolerated with good immunogenicity at 5×10^8 pfu and no severe adverse events. In study VAC037, MVA MSP1 was associated with more side effects when administered at 5×10^8 pfu compared to studies that have used MVA vectors at a dose of 2×10^8 pfu. In the HCV003 study the MVA-NSmut administered at 2×10^8 has shown a good safety profile and the induction of very potent immune responses. A slightly lower dosage (1.8×10^8 pfu) has been chosen for study, aiming to inject a volume of 0.2mL.

4.4.4. Selection and Timing of Dose for Each Subject

The vaccine schedule will consist of a single priming injection with AdCh3NSmut1, followed by a single boost with MVA-NSmut 56 days later in a heterologous prime/boost regimen. Subjects randomized to placebo will receive 2 doses of placebo at Day 0 and Day 56 (approximately week 8). As placebo, a volume of the normal saline equal to the volume of the investigational vaccines will be used.

4.4.5. Blinding

The pharmacist at each site will refer to the Treatment Key provided for the trial by the SDCC to determine the treatment for the subjects. The pharmacist will maintain an open label code (provided by the SDCC) under locked/secured conditions and will follow the randomization code.

Vaccine will be prepared by a pharmacist or trained nurse and administered by a blinded vaccine administrator. All study assessments will be performed by blinded study personnel. All other staff, as well as all subjects, will be blinded to treatment assignment.

Unblinding is unlikely to be necessary for the provision of medical treatment or to otherwise protect the safety of study subjects. In the event that an investigator is concerned that a subject might be put at undue risk by continuing product use, the investigator may discontinue product use by this subject; however, knowledge of the specific product (vaccine or placebo) to which the subject was assigned should not be necessary to guide further follow-up and/or treatment.

The site investigators and/or Independent Safety Monitor (ISM) should be available to review and evaluate any notable reactions. In the case of a medical emergency, the site investigators or ISM may deem it medically necessary to unblind the subject's treatment assignment. If the site investigators or ISM believe that unblinding would benefit the medical care of the subject and time permits, DMID will be consulted prior to unblinding, and concurrence will be obtained.

Otherwise, subjects will be unblinded to their drug only at the close of the trial. Subjects who develop HCV infections or drop out will not be unblinded early. The Data Safety and Monitoring Board (DSMB) may receive data in aggregate and presented by treatment group, but without the treatment group identified. The DSMB may be unblinded to individual study treatment assignments, as needed, to adequately assess safety issues.

4.4.6. Prior and Concomitant Therapy

Concomitant medications will include all current medications and medications taken within the 30 days prior to enrollment (prescription and over-the-counter drugs, vitamins and supplements, topical products, vaccinations, and allergy shots) through 34 days after the second vaccination (approximately Day 90 for subjects who receive both doses of vaccine or approximately Day 30 for subjects who receive only one dose of vaccine) or early termination (if prior to Day 90), whichever occurs first. Assessment of eligibility also will include a review of permitted and prohibited medications (per the exclusion criteria).

Immunosuppressant medications, as defined by exclusion criterion #22, and medications for the treatment of HCV infection will be collected for the duration of the study. Subjects who take such medications will be excluded from the ATP analysis population. See Section 6.3.4 for more details.

Medications that might interfere with the evaluation of the investigational product should not be used unless absolutely necessary. Medications in this category include, but are not limited to, glucocorticoids, i.e., oral, parenteral and high-dose inhaled steroids, and immunosuppressive or cytotoxic drugs. Other than from participation in this study, subjects should not receive experimental agents including vaccines during the 20-month study period. The administration of licensed vaccines should be delayed until 14 days after the last study vaccination. Subjects should also not receive licensed products from participation in another clinical trial. Subjects who take such medications will be excluded from the ATP analysis population. See Section 6.3.4 for more details.

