who exchanged sex with male partner(s) for money or drugs in the past year; and (2) female and in a current relationship with a high risk male (active MSM, HIV positive male).⁸³

- 14. Any other significant disease, disorder or finding, which, in the opinion of the Investigator, may put the subject at risk because of participation in the study, may influence the result of the study, or may influence the subject's ability to participate in the study.
- 15. History of or current diagnosis of Diabetes mellitus.
- 16. History of or current diagnosis of autoimmune disease.
- 17. History of or current cardiac disease including history of myocardial infarction or arrhythmia.
- 18. Current diagnosis of active liver disease.
- 19. History of seizure disorder or currently taking anti-convulsant therapy that would interfere with safety evaluation.
- 20. Uncontrolled hypertension (defined as systolic blood pressure being greater than 140mm Hg or diastolic blood pressure being greater than 90mm Hg).
- 21. History of splenectomy.
- 22. Long term immunosuppressive use (defined as taken for 14 days or more in total at any time during the past 180 days) of high dose oral or parenteral glucocorticoids (high dose defined as prednisone ≥ 20 mg total daily dose, or equivalent dose of other glucocorticoids); or high-dose inhaled steroids (high dose defined as >800 mcg/day of beclomethasone dipropionate or equivalent); or any use of hepatotoxic or non-FDA approved medication.
- 23. Have an acute illness, including an oral temperature greater than or equal to 100.4°F, within 7 days prior to the first vaccination.
- 24. Immunization against another pathogen within 14 days of planned injection.

Second vaccination exclusion criteria:

The following events associated with vaccine immunization constitute absolute contraindications to further administration of vaccine. The subject will not receive additional vaccination, but will continue with scheduled follow-up procedures except vaccination.

- 1. Anaphylactic reaction following administration of vaccine.
- 2. Pregnancy. If a woman reports having a positive home urine pregnancy test or a positive in clinic urine pregnancy test prior to a scheduled second vaccination, she is not eligible to receive the study vaccine. If she later returns to clinic and reports

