7.2 Concomitant Medications/Treatments

Administration of any concomitant medications, therapies or vaccines will be documented in the subject's data collection form and reported on the subject's data acquisition screen. Concomitant medications will include all current medications and medications taken within the 30 days prior to enrollment (prescription and over-the-

counter drugs, vitamins and supplements, topical products, vaccinations, and allergy shots) through 34 days after the second vaccination (approximately Day 90 for subjects who receive both doses of vaccine or approximately Day 30 for subjects who receive only one dose of vaccine) or early termination (if prior to Day 90), whichever occurs first. Assessment of eligibility also will include a review of permitted and prohibited medications (per the exclusion criteria).

Immunosuppressant medications, as defined by exclusion criterion #22, and medications for the treatment of HCV infection will be collected for the duration of the study.

Medications that might interfere with the evaluation of the investigational product should not be used unless absolutely necessary. Medications in this category include, but are not limited to, glucocorticoids, i.e., oral, parenteral and high-dose inhaled steroids, and immunosuppressive or cytotoxic drugs. Other than from participation in this study, subjects should not receive experimental agents including vaccines during the 20-month study period. The administration of licensed vaccines should be delayed until 14 days after the last study vaccination. Subjects should also not receive licensed products from participation in another clinical trial.

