6.3.3. According to Protocol Population

The according to protocol (ATP) population is a subset of the mITT analysis cohort, excluding subjects with major protocol deviations that would compromise the assessment of vaccine efficacy (see list below). Subjects who meet any of the criteria listed below will be censored in time to event analyses according to the date of first occurrence of the criteria, and will be excluded from all other types of analyses. The ATP cohort will exclude subjects who:

- a. receive treatment for acute HCV infection;
- b. were enrolled but subsequently found to have been ineligible at enrollment based on a criterion that could reasonably be expected to affect vaccine efficacy (as reviewed by the blinded clinical review team [see below]);
- c. did not receive both doses of vaccine or control;
- d. acquired HCV infection prior to receipt of the second vaccination;
- e. received the wrong (non-randomized) product at either dose;
- f. received the second dose fewer than 42 days or more than 70 days after the first dose;
- g. received an immunosuppressant other than inhaled or topical steroids;
- h. were immunized against another pathogen or received immunoglobulins or other blood products within 14 days of either dose of study vaccine;
- i. have autoimmune disease; and
- j. have a confirmed or suspected immunosuppressive or immunodeficient state.

Membership in the ATP efficacy cohort will be assessed by a centralized, blinded, clinical review team comprised of the site PIs and the sponsor prior to unblinding of the study data.

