6.3.4. Immunogenicity Population

The immunogenicity analysis population will consist of all subjects who received any study product and for whom immunogenicity endpoint data are available. If a subject does not receive the second dose, the subject will not be included in the Post-Dose 2 analyses. In the unlikely event of an error in randomization or study product administration (i.e., incorrect product), subjects will be grouped by the product they actually received. In the unlikely event that a subject receives one dose of vaccine and one dose of placebo, the subject will be excluded from immunogenicity analyses.

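### SAP 4.4.6 excludes users of HCV drugs and other listed medications from the ATP population, where SAP 6.3.3 and the protocol censor; read literally, it removes primary events already met

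*SAP*

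**What the plan says.** SAP 4.4.6 repeats two paragraphs of protocol 7.2 and adds a consequence to each.

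- The first paragraph is about data collection: "Immunosuppressant medications, as defined by exclusion criterion #22, and medications for the treatment of HCV infection will be collected for the duration of the study". The SAP then adds "Subjects who take such medications will be excluded from the ATP analysis population".
- The second paragraph lists drugs to avoid (steroids, including high-dose inhaled ones, and immunosuppressive or cytotoxic drugs), experimental agents, early licensed vaccines and products from other trials. It ends with the same added sentence.
- Both paragraphs close with "See Section 6.3.4 for more details". Section 6.3.4 begins "The immunogenicity analysis population will consist of all subjects who received any study product" and says nothing about ATP.

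The ATP population is defined in SAP 6.3.3, which follows protocol 11.4.1. Criterion (a) is treatment of acute HCV. Criterion (g) is having "received an immunosuppressant other than inhaled or topical steroids". Subjects who meet a criterion "will be censored in time to event analyses according to the date of first occurrence of the criteria", and are left out only of other kinds of analysis. SAP 3.3.7 and 6.5 also censor at first HCV treatment. SAP 8.1 makes the primary analysis a time-to-event analysis in the ATP cohort.

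**The concern.** Two sections of one SAP decide membership of the primary population differently, and 4.4.6 sets no timing condition and does not mention censoring.

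The HCV-drug part matters most. In practice only infected subjects take HCV drugs, so a rule that drops everyone who takes them acts on the outcome. A subject who has already met the endpoint and is treated afterwards would lose that event. Protocol 8.3 provides a treatment referral at every RNA-positive visit, so the situation is foreseeable.

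ATP membership is settled by site investigators and the sponsor. They are blinded to arm, but sites tell subjects that they are infected (protocol 8.3.1). Two competing rules leave avoidable discretion to people who can know infection status.

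**Working it through.** **The two rules side by side**

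| Item | SAP 4.4.6 | SAP 6.3.3 and protocol 11.4.1 |
|---|---|---|
| HCV drugs | Any, at any time in the study | Treatment of acute HCV, criterion (a) |
| Inhaled steroids | High-dose covered: criterion 22 includes "or high-dose inhaled steroids", and the second paragraph names them | Exempt under (g) |
| Experimental agents, other-trial products | Covered by the second paragraph | No such criterion |
| Consequence | Subject excluded | Censored at first occurrence in time-to-event analyses |

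**Where an event can be lost**

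The month-6 sample falls on days 159 to 201 after infection (SAP 3.3.2). Infected subjects leave after H09, target day 270, window 249 to 291 (SAP 6.2). The interval between the two is 270 − 180 = 90 days at target, with extremes of 249 − 201 = 48 and 291 − 159 = 132 days.

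- *Endpoint met at day 180, HCV drugs started before H09.* Under SAP 8.1 this is an event dated at the month-6 sample. Under 6.3.3 any censoring date falls after the event and changes nothing. Under 4.4.6 the subject is gone.
- *HCV drugs started before the month-6 sample.* Under 6.3.3 the subject is censored at first treatment. Under 4.4.6 the subject is gone. No event had been reached, so only follow-up time is lost.

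**The plan's own figure**

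Inputs from SAP 5: 43 events, hazard ratio 0.40, two-sided alpha 0.05, 1:1 allocation, 14 and 5.6 cases per 100 person-years, 292.5 ATP subjects, 1.5 years.

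- Expected events = 292.5/2 × 1.5 × (0.14 + 0.056) = 43.0.
- Power (Schoenfeld) = Φ(√d/2 × |ln 0.40| − 1.96). At d = 43: Φ(3.279 × 0.916 − 1.96) = Φ(1.044) = 85.2%.

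The stated 85% reproduces.

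**Effect of literal exclusion**

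The share of events followed by HCV treatment before H09 is not in the documents. The range below is assumed, with losses rounded to whole events.

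| Share of 43 events removed (assumed) | Events left | Power |
|---|---|---|
| 0% | 43 | 85.2% |
| 5% (about 2) | 41 | 83.5% |
| 15% (about 6) | 37 | 79.6% |

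Removing the same share from each arm leaves the hazard ratio at 0.40. With shares qv (vaccine) and qp (placebo) it becomes roughly 0.40 × (1 − qv)/(1 − qp). Illustratively, 5% and 20% give 0.40 × 0.95/0.80 = 0.475, and 20% and 5% give 0.40 × 0.80/0.95 = 0.337.

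For the steroid and experimental-agent conflicts the number of subjects is also unknown. Every 10 ATP subjects dropped carry 10 × 1.5 × 0.098 = about 1.5 expected events, where 0.098 is the mean of the two annual rates.

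**The case against.** The best defence is that 4.4.6 is a summary, not a definition. It sits in the investigational plan and defers elsewhere for detail. SAP 6.3.3 itself speaks of excluding subjects and then explains that, for time-to-event analyses, this means censoring. SAP Table 6 lists acute-HCV treatment as an exclusion reason, while Listing 1 carries a censoring day. Protocol 11.4.1 and SAP 3.3.7, 6.3.3 and 6.5 all censor. Membership is reviewed blind before unblinding, and the analysis is repeated in mITT, which 4.4.6 does not touch.

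Much of this stands: a careful programmer would probably censor. But the deferral goes to the wrong section, so it never leads to the censoring rule. The two sentences are not in protocol 7.2, and SAP 14 does not list them as a change. The lists of drugs also differ, which no reading of the word excluded repairs.

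Four stronger readings are tempting but unsupported:

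- *Events are also lost to treatment after the study.* Infected subjects exit after H09 (protocol 8.3), and HCV drugs are collected only during the study.
- *All of criterion 22 is imported, including* "any use of hepatotoxic or non-FDA approved medication". Section 4.4.6 speaks of immunosuppressants as defined by that criterion, so whether this clause comes along is unclear.
- *Short steroid courses go unrecorded after Day 90.* Protocol 7.2 and SAP 4.4.6 tie collection to criterion 22, but the Day 120 visit text (protocol 8.2.9) and Appendix C note B record immunosuppressants with no dose or duration limit. The wording is inconsistent, which does not establish a gap in the data.
- *A known number of events will be lost.* Uptake is not given, and protocol 2.1 describes access to and completion of treatment as low.

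**Conclusion.** The conflict is real and concerns the primary population. As written, 4.4.6 states a rule that 6.3.3 and the protocol contradict on which drugs count and on what follows from taking them. If it were followed, the loss would be limited to subjects who meet the endpoint and start HCV drugs between the month-6 sample and H09, but it would be outcome-dependent.

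The power range of 83.5% to 79.6%, against 85.2%, rests wholly on the assumed 5 to 15%. Nothing in the documents indicates different removal by arm, so the hazard-ratio figures show only how the error would act. This should be corrected before unblinding. It does not undermine the design, because under 6.3.3 the events stay in.

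**What to change.** 1. Delete both ATP exclusion sentences in SAP 4.4.6, make 6.3.3 the sole ATP definition, and correct the pointer from 6.3.4 to 6.3.3.
2. State in 6.3.3 that HCV treatment or immunosuppressant use after baseline censors at first use and never removes an event already met. Word Table 6 to match.
3. Reconcile the inhaled-steroid and experimental-agent wording with protocol 11.4.1, including its criterion (g), keeping non-steroid immunosuppressants covered. This review proposes no dose threshold. Any criterion beyond the protocol's list should be recorded in SAP 14.
4. Reconcile the collection wording: limited to criterion 22 in protocol 7.2 and SAP 4.4.6, unrestricted in protocol 8.2.9 and Appendix C.

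Items 1 and 2 are SAP wording only: no new data and no change to the stated design. Items 3 and 4 need a decision from the study team, and item 4 a check of what the sites recorded.
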